11.3 Assessment of the Secondary Endpoints

This secondary endpoint is the mean number of anti-glaucoma medications and surgical success in the porous plate group as compared to the silicone plate group at 12 months. The baseline number of medications will be compared to check for statistically significant differences and, if needed, a change from baseline analysis will be performed. The statistical significance of the differences in the number of medications will be determined using two-tailed paired t-tests. The mean number of medications at individual time points will be compared in the two groups. Kaplan-Meier survival analysis will be performed for statistical analysis of success rates, with comparisons of groups using the log rank test. Complications will be compared using comparison of proportions (z) test.

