Glaucoma drainage devices are helpful in the management of intractable glaucoma, which does not respond well to conventional medical and surgical therapies. The Ahmed Glaucoma Valve is a glaucoma drainage device that has a flow-resistive valve mechanism.¹⁻³ This valve is helpful in minimizing postoperative hypotony and complications associated with hypotony, including flat anterior chamber, choroidal effusions, and suprachoroidal hemorrhage.^{4,5}

After Ahmed Glaucoma Valve implantation, patients may require adjunctive anti-glaucoma medications for adequate control of intraocular pressure.^{4,6} With smaller glaucoma valve implants, such as the Molteno implant, increasing the device surface area may lead to lower mean intraocular pressure and fewer adjunctive glaucoma medications.^{7,8} However, additional surface area does not dramatically improve the results with larger implants, such as the Ahmed Valve and the Baerveldt implant.⁹⁻¹² In contrast with trabeculectomy, use of adjunctive mitomycin C does not appear to improve the results with the Ahmed Glaucoma Valve.¹³

In experimental studies, different glaucoma drainage implant plate materials may influence capsule formation and influence the results of glaucoma drainage implants.^{14,15} In clinical comparisons, different plate materials have been associated with significant difference of mean postoperative intraocular pressure in some¹⁶⁻¹⁸ but not in all studies.^{19,20} In a randomized prospective trial, transient elevation of intraocular pressure during the early postoperative period,

known as a "hypertensive phase," was less frequent after silicone plate compared with polypropylene plate Ahmed Glaucoma Valve implantation.¹⁶ In addition to implant plate size and material, other variables influencing success of glaucoma drainage implant surgery have been identified, including race, treatment with silicone oil endotamponade, and neovascular glaucoma.²¹

A silicone plate Ahmed Glaucoma Valve has demonstrated efficacy and safety in clinical studies.¹⁶⁻²⁰ An Ahmed Glaucoma Valve plate constructed with porous material, which is Food and Drug Administration (FDA) approved, but has not been studied in clinical trials, may offer advantages in reducing encapsulation of the implant, thereby potentially improving postoperative intraocular pressure control.

2. Device Description

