10.1 Anticipated Adverse Events

Anticipated adverse events include those that might reasonably be expected to occur in this study because they are associated with glaucoma surgical procedures. Anticipated adverse events for both the porous plate and silicone plate glaucoma valves include:

- * Wound Leak
- * Shallow Anterior Chamber

- * Flat Anterior Chamber
- * Choroidal effusion
- * Exposure of Tube, Patch Graft, Plate
- * Severe Inflammation
- * Tube and/or Flow Obstruction
- * Corneal Edema
- * Motility Disturbance (i.e. Diplopia)
- * Suprachoroidal hemorrhage
- * Hypotony (≤ 5 mmHg)
- * Elevated intraocular pressure
- * Retinal Detachment

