10.7 Aggregate Review of Adverse Events

The Medical Monitor will be responsible for the continuous review of unanticipated adverse events.

11. Statistical Considerations

This prospective, two-arm, unmasked, randomized, controlled trial will evaluate and compare the clinical outcomes after implantation of the porous plate (polyethylene) Ahmed Glaucoma Valve (M4) with the silicone plate Ahmed Glaucoma Valve (FP7) in patients with intractable glaucoma. Subjects will be randomized in a 1:1 ratio to one of two surgical intervention arms - surgical intervention with the Model FP7, Silicone Plate Ahmed Glaucoma Valve (Group A) or the Model M4, Porous Plate Ahmed Glaucoma Valve (Group B). The computer-generated randomization scheme (using varying block sizes of 2 to 4) will be completed by a staff member of the University of Virginia, Department of Ophthalmology, whose sole role in this study is to generate the randomization scheme. The subject surgical intervention arm assignment will be placed in a sealed envelope, securely delivered to the sites, and will be accessed by the site study staff in the site Surgical Admission Suite immediately prior to local anesthesia injection for the surgical procedure. Post-randomization, the assigned surgical intervention arm will be unmasked to the subject.

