11.1 Sample Size Considerations

With a sample size of 40 in each group, the power of the study will be 0.8 (80%) to detect a 1.5 mmHg difference in intraocular pressure with a standard deviation of 3 mmHg. Investigators will screen and treat patients until the study is fully enrolled or the study is terminated. All subjects undergoing surgical intervention will be entered in the statistical analysis. Based on prior studies, failure to complete the 12 month post-operative period is not likely to exceed 10% of randomized subjects.

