11.2 Assessment of the Primary Endpoint

The primary efficacy endpoint is the mean intraocular pressure in the porous plate group as compared to the silicone plate group at 12 months. The analysis will compare the changes of intraocular pressure after the surgical intervention in the porous plate group as compared to the silicone plate group. Baselines will be compared to check for statistically significant differences and, if needed, a change from baseline analysis will be performed. The statistical significance of the differences in intraocular pressure will be determined using two-tailed paired t-tests.

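### With about 40 eyes per arm, complications should be reported as risk differences with 95% intervals, not by a large-sample z test alone

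*Combined protocol and SAP*

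**What the plan says.** Section 11.3 gives one inferential method for complications: "Complications will be compared using comparison of proportions (z) test". It does not say whether the variance is pooled, whether a continuity correction applies, or what happens when counts are small. Two-sidedness is stated for the pressure and medication comparisons ("two-tailed paired t-tests" in section 11.2, and the same in 11.3) but not for complications. No significance level is given anywhere.

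Section 10.1 opens its list with "Anticipated adverse events for both the porous plate and silicone plate glaucoma valves include" and names 13 types, with no expected rate for any of them. Section 11.6 adds a tabulation of adverse events by type and severity. Section 11.5 has the Medical Monitor review unanticipated events against a 30% threshold. Neither provides a between-arm estimate or an interval.

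Section 11.1 plans 40 subjects per group, sized "to detect a 1.5 mmHg difference in intraocular pressure with a standard deviation of 3 mmHg". The introductory background says that the porous plate "has not been studied in clinical trials".

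**The concern.** A test of two proportions that relies on the normal approximation is being applied to arms of about 40, for a list that includes events such as suprachoroidal hemorrhage and retinal detachment. Two things are at stake.

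- **Precision.** The sample was sized for a mean pressure difference. A p-value for a complication does not tell the reader how large an excess on the new plate the data still allow. By the document's own account the porous plate had no earlier trial data, so this comparison would be early randomised evidence on its safety.
- **Dependence on the approximation.** When a split is sparse and close to 0.05, whether it is called significant can turn on which test is used. The plan names the one that gives the smallest p-value in the examples below, and gives no rule for small counts.

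**Working it through.** **Inputs.** n = 40 per arm (section 11.1) and 1:1 allocation (opening of section 11). Two-sided alpha of 0.05, pooled variance and no continuity correction are assumed, because the document does not state them. *Complications* is taken to mean the 13 types in section 10.1. Event rates are assumed over a range.

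**The plan's own figure.** There is none for complications. The 80% power in section 11.1 refers to mean pressure and does not carry over. (It does not reproduce for two independent groups either: 1.5 / (3 × √(2/40)) = 2.236; 2.236 − 1.960 = 0.276; power about 61%. That is a separate matter.)

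**1. Sparse splits.** z = (p1 − p2) / √[p̄(1 − p̄)(2/n)].
- 6 v 1: p̄ = 7/80 = 0.0875; z = 0.125 / √(0.0875 × 0.9125 × 0.05) = 0.125 / 0.0632 = 1.978.
- 4 v 0: p̄ = 4/80 = 0.05; z = 0.100 / √(0.05 × 0.95 × 0.05) = 0.100 / 0.0487 = 2.052.

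Barnard's p-value is the probability of a pooled |z| at least this large, maximised over the unknown common rate.

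| Split (of 40) | z | Barnard | Boschloo | Fisher | Newcombe 95% interval, points |
|---|---|---|---|---|---|
| 6 v 1 | 0.048 | 0.059 | 0.070 | 0.108 | −0.6 to 26.7 |
| 4 v 0 | 0.040 | 0.043 | 0.082 | 0.116 | −0.6 to 23.1 |

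Section 11.4 allows up to 84 treated, or 42 per arm. The picture is the same there: 6 v 1 gives z 0.048 and Barnard 0.060; 4 v 0 gives 0.040 and 0.044.

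**2. True type I error of the z test.** Sum the binomial probabilities of all 41 × 41 tables with z-test p < 0.05, at a common event rate.

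| Common rate | 1% | 2.5% | 5% | 7.5% | 10% | 12.5% |
|---|---|---|---|---|---|---|
| True size | 0.1% | 1.3% | 4.3% | 5.7% | 5.9% | 5.6% |

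The maximum is about 5.9%, near a rate of 9%. The size passes 5% at a rate of about 6%.

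**3. Power of the z test, by the same enumeration.** 2.5% v 7.5%: 16%. 5% v 10%: 15%. 5% v 15%: 35%. By the usual normal-approximation formula, 80% power for 5% v 15% would need 141 per arm.

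**4. What the data could still allow.**
- 0 of 40: exact upper 95% limit = 1 − 0.025^(1/40) = 8.8%.
- 2 v 2: the Wilson limits for 2/40 are 1.4% and 16.5%, so the Newcombe half-width is √[(0.050 − 0.0138)² + (0.165 − 0.050)²] = 0.121, or ±12.1 points.
- 0 v 0: the z statistic is 0/0 and gives nothing to report, while the Newcombe interval is ±8.8 points. The chance of no event in either arm is 0.99^80 = 45% at a true rate of 1%, and 0.975^80 = 13% at 2.5%.

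**The case against.** The strongest reply is that the z test does little harm. Its true size exceeds 5% by at most 0.9 points, and for the rarest events it is conservative. Barnard's test agrees with it at 4 v 0. Much of the gap to Fisher reflects Fisher's own conservatism: its true size is only 0.03% to 2.2% at common rates of 2.5% to 12.5%. A reader might infer from the table that the z test makes p-values too small in general and so inflates false positives. The enumeration does not support that, and this part of the reply stands.

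It is also fair to say that low power comes from the sample size and that no choice of test cures it. An exact test lowers power further. The document gives no complication rates, and some listed events, such as elevated intraocular pressure, may well be common. Complications are not among the endpoints in sections 5.1 and 5.2, and the tabulation and Medical Monitor review are real safeguards. All of this stands, and it limits how serious the point is.

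A reader might also infer that a non-significant result says nothing about safety, or that the plan means to read it as equal safety. Neither follows. A 2 v 2 result excludes differences beyond about 12 points, and the document nowhere makes an equal-safety claim.

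The reply does not answer the absence of any estimate or interval. That gap does not depend on which test is preferred.

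**Conclusion.** The point holds as a question of precision and reporting, and not as one of serious error inflation. The plan offers only a p-value for comparisons that have about 35% power for a rise from 5% to 15%, that cannot exclude a rate of 8.8% after zero events, and that leaves about ±12 points open at 2 v 2. Dependence on the approximation is a lesser matter, confined to borderline sparse splits: 6 v 1 changes side of 0.05 under all three exact tests, whereas 4 v 0 does so under Fisher and Boschloo but not Barnard.

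These results assume 40 per arm, two-sided 0.05, a pooled z statistic, and complications uncommon enough to give sparse counts. No primary or secondary endpoint conclusion is affected. This is an inexpensive improvement worth making before analysis.

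**What to change.** Replace the complications sentence in section 11.3 with:

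*For each complication, the number and percentage of eyes per arm, the risk difference and its 95% Newcombe interval will be reported; any p-value will come from the unconditional exact test based on the pooled z statistic (Barnard).*

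This keeps the planned statistic, settles the variance form, and gives a reportable result when neither arm has an event. Standard software does it, and no visit, procedure or sample size changes.

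The costs are small. P-values near 0.05 are slightly larger (0.059 for 0.048 at 6 v 1; 0.043 for 0.040 at 4 v 0). Enumerated power at 5% v 15% falls from about 35% to about 30%. The interval and the p-value can also disagree at the margin: at 4 v 0 the Newcombe interval just includes zero while Barnard's p is 0.043. The text should therefore lead with the interval.

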11.4 Accrual

Maximum study accrual is estimated to be 88 subjects to accrue the targeted 80 subjects required to meet the study objectives. Maximum accrual allows for a 5% ineligibility rate and a 5% rate of coming off study before the planned surgical intervention. Once target accrual is reached, the study allows those within the screening process to be enrolled. As this allowance is not to exceed 4 patients, up to 84 patients may be treated with Ahmed Glaucoma Valves. Based upon accrual rates to prior drainage

implant studies, accrual is estimated at 15 per month; thus, accrual to the study should be completed in less than 6 months.

11.5 Plans for Interim Analysis

There will be no formal interim analysis. However, for purposes of safety and surgical failures only, unanticipated adverse events will be reviewed periodically by the Medical Monitor to detect a statistically significant increase of vision-threatening complications (e.g., suprachoroidal hemorrhage, endophthalmitis, and surgical failures). If vision-threatening complications and surgical failures exceed a threshold of 30% during the study, consideration will be given by the Medical Monitor to terminate the study early.

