9.4 Device Explant, Repositioning, or Replacement

The device may be revised, repositioned, removed, or replaced by the same kind of device or another marked drainage device if the original device was damaged or determined to be not functioning. If surgical intervention for repositioning or replacement is required, the subject will be required at a minimum to complete all of the protocol required post-operative visits. If sequelae persist, the subject should be followed until all sequelae are considered to be stabilized or resolved.

10. Safety

At each visit, the ocular health of the subject will be assessed. The cornea, anterior chamber, trabecular meshwork, device implant location (if available), and fundus will be examined. Any ocular unanticipated adverse events occurring during the study whether they are considered to be device related or not, must be documented on the Adverse Event Case Report Form. Date and time of the event, event severity, treatment (if any), and the assessed relationship of the event to the study devices will be recorded on the Adverse Event Case Report Form. Conditions that exist at the time the subject is enrolled in the study do not need to be recorded on the Adverse Event Form as adverse events, unless they increase in severity during the study and constitute an unanticipated adverse event..

The collection and recording of unanticipated adverse events will begin at the start of the surgical intervention and will end at the subject's Month 12 or Early Termination Visit. Unanticipated adverse events must be followed until the adverse event has recovered or recovered with ongoing sequelae that will likely not change in the view of the investigator. This period *may* extend beyond study termination.

A brief overview of the differences between anticipated, unanticipated and serious adverse events is provided.

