10.2 Unanticipated Adverse Events

Unanticipated adverse events include any serious adverse effects on health or safety or any life-threatening problem or death caused by or likely directly related to the Ahmed Glaucoma Valve (M4 or FP7) or the placement of the Ahmed Glaucoma Valve (M4 or FP7) within the eye that are not typically associated with glaucoma surgical procedures.

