10.3 Serious Adverse Events

Serious adverse events include those events that require (≥ 24 hours) or prolong hospitalization, require surgical intervention, are sight or life-threatening or fatal, or result in significant disability or incapacity.

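### The Medical Monitor's review is limited to unanticipated adverse events, yet 11.5 expects it to detect complications and failures that 10.1 lists as anticipated

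*Combined protocol and SAP*

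**What the plan says.** Section 11.5 rules out a formal interim analysis but keeps a safety review: "unanticipated adverse events will be reviewed periodically by the Medical Monitor to detect a statistically significant increase of vision-threatening complications (e.g., suprachoroidal hemorrhage". Its other two examples are endophthalmitis and surgical failures. The next sentence says that if vision-threatening complications and surgical failures pass 30%, the Medical Monitor will consider ending the study early. Sections 10.7 (aggregate review) and 11.7 (termination) also describe the Monitor's review as one of unanticipated adverse events.

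The terms are set in Section 10:

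- 10.1 lists 13 anticipated events for both valves. They include "Suprachoroidal hemorrhage", "Elevated intraocular pressure", and hypotony at 5 mmHg or below.
- 10.2 describes unanticipated events as "any serious adverse effects on health or safety or any life-threatening problem or death". They must also be attributable, at least probably, to the device "or the placement of the Ahmed Glaucoma Valve (M4 or FP7) within the eye that are not typically associated with glaucoma surgical procedures".
- 10.3 counts as serious, among others, events that "require surgical intervention, are sight or life-threatening or fatal".
- 10.5 sends serious events to the Medical Monitor within 24 hours and all adverse events to the Institutional Review Board. It requires the Adverse Event form, submitted to the coordinating site, for unanticipated events.

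Section 11.6 gives four examples of treatment failure (increased IOP, hypotony, loss of light perception, additional glaucoma surgery) and says that failures are entered in the study database. Section 5.2(b) defines surgical success at 12 months, with IOP above 5 and below 22 mmHg.

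**The concern.** The input to the review and its purpose are described in terms that exclude each other. An event on the 10.1 list is there because it is associated with glaucoma surgery; an event under 10.2 must not be typical of it. A review confined to 10.2 events therefore leaves out suprachoroidal hemorrhage, the first example that 11.5 asks it to detect, and failures by high or low IOP.

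What is at stake is monitoring during the trial. The Medical Monitor is the only reviewing role that the protocol describes for this purpose, and the background section says that the porous plate, although FDA-approved, has not been studied in clinical trials. The 30% sentence does not itself say unanticipated, but 11.5 names no other source of data. If the percentage is taken from the review as described, events that belong in the numerator may be missing.

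**Working it through.** **1. Follow each named event through the definitions.** The first two rows are examples in 11.5; the other four are the failure examples in 11.6. Reading the surgical failures of 11.5 as the treatment failures of 11.6 is an assumption, because 11.5 does not define its term.

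| Event | On the 10.1 list? | Unanticipated under 10.2? | Serious under 10.3? | Stated route to the Monitor |
|---|---|---|---|---|
| Suprachoroidal hemorrhage | Yes, by name | No | Yes, if sight-threatening or needing surgery | 24-hour report |
| Endophthalmitis | No | Possibly; not settled by the text | Yes, if sight-threatening | 24-hour report; periodic review if unanticipated |
| Increased IOP | Yes | No | Only if it meets 10.3 | None when not serious |
| Hypotony | Yes | No | Only if it meets 10.3 | None when not serious |
| Loss of light perception | No | Not settled by the text | Yes | 24-hour report |
| Additional glaucoma surgery | No | Not settled by the text | Yes, surgical intervention | 24-hour report |

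One of the three examples in 11.5 is on the 10.1 list by name, and a second (surgical failures) is on it in part. Two of the four failure examples in 11.6 are on it.

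**2. What remains after serious-event reporting.** Two things:

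- The 24-hour reports are individual notifications. No section says that they form part of the periodic review in 10.7, 11.5 or 11.7.
- A non-serious failure by IOP alone is outside 10.2 on two counts (anticipated, and not serious) and outside 10.3. Its stated destinations are the Institutional Review Board (10.5) and the study database (11.6). Neither section says that it goes on to the Monitor.

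**3. Does 11.5 mean to count such a failure?** The text points both ways. The sentence on the periodic review makes surgical failures an example of vision-threatening complications, which suggests only the sight-threatening ones. The 30% sentence names failures beside those complications, which suggests a separate and wider group.

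**4. What the 30% means as a count.** The protocol does not derive the figure, so there is nothing to reproduce. To exceed 30% of N, the count must be the smallest whole number above 0.30 × N:

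- N = 80 (target, 11.4): 0.30 × 80 = 24, so 25 (25/80 = 31.3%).
- N = 84 (maximum treated, 11.4): 0.30 × 84 = 25.2, so 26 (26/84 = 31.0%).
- N = 40 (one arm): 0.30 × 40 = 12, so 13 (13/40 = 32.5%).

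Section 11.5 does not say which denominator applies.

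**5. Sensitivity to incomplete capture (illustration only).** Take N = 80, at most one counted event per subject, an assumed true rate p and an assumed captured share f. The chance that the observed count reaches 25 is P(X ≥ 25), with X binomial (80, p × f).

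| Assumed p | f = 1 | f = 0.75 | f = 0.5 |
|---|---|---|---|
| 0.40 | 0.958 | 0.445 | 0.011 |
| 0.35 | 0.793 | 0.186 | 0.002 |

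The documents give neither p nor f. The table shows only that a threshold of this kind reacts strongly to missing events, not that events would be missed to this extent here.

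**The case against.** The strongest reply is that serious-event reporting already does most of the work. Section 11.5 itself treats suprachoroidal hemorrhage as vision-threatening; 10.3 makes sight-threatening events serious; and 10.5 puts serious events before the Monitor within 24 hours. Loss of light perception and reoperation travel the same way. Nothing stops a Monitor who holds these reports from counting them, and 11.7 lets the Monitor end the study as necessary. Section 11.5 also opens its review sentence by naming safety and surgical failures as the purpose, so failures were clearly meant to be looked at. The Manual of Procedures, cited in 10.5, is not among the documents and may supply the missing route.

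Most of this stands, and it limits the point. A reader might infer that the Monitor cannot see suprachoroidal hemorrhage, or that the trial has no working safety oversight. The documents do not support either inference, because 10.3 and 10.5 provide a direct and fast route for serious events. A reader might also infer that the 30% figure is bound to be understated. That does not follow: it depends on whether the Monitor counts only what the review is described as covering, and on whether 11.5 means to include non-serious IOP failures at all.

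Timing is a further limit. Section 5.2(b) sets success at 12 months, so on one reading an IOP failure is not classified until then. The Kaplan-Meier analysis in 11.3 implies earlier failure times, so the text leaves this open.

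What the reply does not remove is the wording itself. Three sections give the review a scope that excludes its own first-named target, and a manual would not change what they say.

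**Conclusion.** The point holds as an internal inconsistency of modest severity. Sections 10.7, 11.5 and 11.7 cannot be followed literally together with 10.1 and 10.2 if the review is to do what 11.5 asks.

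The practical gap is narrower than the wording suggests. Serious events reach the Monitor but are not placed in the periodic review, and non-serious failures by IOP alone have no route to the Monitor in the documents supplied. Any effect on the 30% figure would be to make it too low, if it is taken from the review as described. Its size cannot be estimated.

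Endpoint analyses are not affected: complications are assessed at every post-operative visit (8.3) and compared between groups at the end (11.3). Passing 30% leads only to consideration of termination, not to a stop. The conclusion on wording rests on the text alone. The conclusion on the missing route assumes that the Manual of Procedures does not fill it.

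**What to change.** Reconcile 10.7, 11.5 and 11.7 with 10.1 to 10.3, so that the periodic review covers vision-threatening complications and surgical failures whether anticipated or not. Say that it draws on the reported serious adverse events and on the treatment failures already entered in the database under 11.6. If the Manual of Procedures already carries non-serious IOP failures to the Monitor, a cross-reference is enough for that part.

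In 11.5, the sponsor and the Medical Monitor should state:

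- which failures count, starting from 5.2(b) and 11.6, and from what time a failure is classified;
- which denominator the 30% uses, and whether it is pooled or per arm.

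The threshold and any stopping decision stay with the sponsor and the Medical Monitor.

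The cost is protocol wording and a periodic tabulation of data already collected. No visit or procedure is added.
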